7. OVERALL DESIGN

7.1. Trial Design

7.1.1. Trial Objective

The primary objective of this study is to evaluate the effectiveness and safety of the NeuWave Certus Microwave Ablation System and Accessories in the percutaneous microwave ablation of NSCLC or oligometastatic lung tumor.

7.1.2. Trial Method Selection and Its Rationale

This is a prospective multicenter study with single-arm performance goal. The prospective study design can reduce bias and provides better data accuracy without any needs for recall. A single-arm design with performance goal is adopted. Due to the lack of published objective performance criteria (OPC), the performance goal (PG) is constructed as the target value. The statistical considerations are to calculate point estimate of the primary study endpoint and its corresponding

95% confidence interval. This 95% confidence interval will be compared with clinically significant PG predefined in the protocol to determine whether this investigational product has reached the minimum standards recognized in the professional field. Based on the scientific hypothesis that the primary endpoint is superior to PG, and the permissible type I and type II errors, the correspondingly required sample size will be estimated to ensure statistical significance of the results.

[figure not shown]
7.1.3. Measures to Reduce and Avoid Bias

This study adopts a prospective design to avoid possible bias of retrospective study. The Independent Review Committee (IRC) will be set up for the determination of key endpoints in order to standardize and unify the evaluation methods, and to avoid potential bias caused by surgeon's judgment.

This study collects data on objective indexes, and all relevant study data will be recorded in the original medical records for inspection and verification during the monitoring process. All investigators will receive proper training to ensure that they are familiar with this study device before their study sites are initiated, and to ensure scientific attitude of the study personnel. In addition, each study site will set a run-in period to include the first 2 subjects treated at this site, but these subjects will be included in the safety set only. This is intended to reduce operational bias due to learning curve.

The investigator should have more communication with the subjects to improve subject compliance. This will help reduce the informational bias.

7.1.4. Investigational Medical Device

	Study Device Composition 1 Certus Microwave Ablation System	Study Device Composition 2 Certus microwave ablation probe
Figure		
Entering global market (year)	Global: 2011	Global: 2011

	Study Device Composition 1 Certus Microwave Ablation System	Study Device Composition 2 Certus microwave ablation probe								
Indications	Certus Microwave Ablation System and accessories are applicable for soft tissue ablation (coagulation) in percutaneous, open surgery and laparoscopic surgery.	Certus disposable microwave ablation probe is a dedicated accessory of Certus Microwave Ablation System, and applicable for soft tissue ablation (coagulation) in percutaneous, open surgery and laparoscopic surgery.								
Components	It consists of a generator, a PDM (probe interface unit, connected to ablation antenna of the system), a temperature measurement system, a cooling system using CO ₂ gas cylinder (the cylinder is not included in the registration device), software and CT brackets.	It consists of a handle (with LED indicator), coaxial connector, cable, ablation probe shaft, microwave radiation tip, 3 temperature sensors, and a CO ₂ circulation loop.								
Dimension	Width: 23" (58.4 cm) Depth: 28" (71.1 cm) Height (including display): 52" (132 cm) (minimum), 59" (150 cm) (maximum) Weight: ~250 pounds (113 kg)	Certus PR and Certus LK models use 17 gauge and 15-gauge probes. Certus LN model uses a 17-gauge probe. All models of probes have 15 cm and 20 cm in length.								
Material	NA	
 
 Ablation probe	Titanium (except for PR ablation probe); titanium, aluminum coating (PR ablation probe)	
 
 Ablation probe shaft, radiation zone, tissue loc area, insertion depth mark, cauterize stop mark	Zirconia, FEP heat shrink tubing (whole body, except for antenna)	
 
 Handle, LED light	ABS resin	
 
 Protective sheath	Polypropylene	
 
	Ablation probe	Titanium (except for PR ablation probe); titanium, aluminum coating (PR ablation probe)	Ablation probe shaft, radiation zone, tissue loc area, insertion depth mark, cauterize stop mark	Zirconia, FEP heat shrink tubing (whole body, except for antenna)	Handle, LED light	ABS resin	Protective sheath	Polypropylene
Ablation probe	Titanium (except for PR ablation probe); titanium, aluminum coating (PR ablation probe)									
Ablation probe shaft, radiation zone, tissue loc area, insertion depth mark, cauterize stop mark	Zirconia, FEP heat shrink tubing (whole body, except for antenna)									
Handle, LED light	ABS resin									
Protective sheath	Polypropylene									

7.1.5. Selection of Subjects:

1) Inclusion criteria

Subjects will be included if ALL of the following inclusion criteria are met:

1. Signed the informed consent form and willing to fulfill the study-related assessments and procedure schedule.
2. Lung tumor patients \geq 18 years of age who are ineligible for/decline surgery and who plan to receive microwave ablation therapy.
3. ECOG performance status score of 0-2.
4. Patients with stages IA1-IA2 NSCLC with documented results from a biopsy or patients with clinically diagnosed oligometastatic lung tumor.
5. Tumor(s) to be ablated in a single surgery should be a maximum of one NSCLC tumor or a maximum of three ipsilateral oligometastatic lung tumors.
6. Tumor(s) to be ablated in a single surgery should be \leq 2cm, locate in the outer two-thirds of a lung, not closer than 1cm from the hilum of lung, great vessels, principal bronchus, trachea or esophagus, and not contiguous with the pleura.

2) Exclusion Criteria

Subjects who meet ANY of the following exclusion criteria will be excluded:

1. Pregnant or breast-feeding.
2. Patients with implantable pacemakers or other electronic implants.
3. Oligometastatic tumors patients whose primary lesion cannot be controlled or have widely metastases, in the opinion of the investigator and/or treating oncologist.
4. Any planned concurrent procedure at the time of ablation.
5. Planned treatment for other tumors in the same side lung during the study period.
6. With a skin infection or ulceration at the site to be punctured by probe(s).
7. Clinical or imaging findings consistent with an active pulmonary infection.
8. Patients with severe pulmonary fibrosis in the area intended to ablate, especially drug-induced pulmonary fibrosis.
9. Patients with prior radiotherapy in the area intended to ablate.
10. Patients with uncontrolled malignant pleural effusion at the lung side with tumor to ablate.
11. Tumors where the anticipated zone of ablation would encompass significant (in the opinion of the treating physician) emphysematous or bullous disease.
12. The investigator anticipates that the ablation zone of the multiple tumor(s) to be ablated

may have overlapping ablation zones.

13. Patients who have received lung ablation or surgical resection therapy within 30 days prior to the ablation procedure under study and those who plan to receive lung tumor ablation or surgical resection therapy or radiation therapy on the ablated lung side before completing the primary efficacy endpoint assessment approximately 30 days after the ablation procedure.
14. Patients who received systemic therapy such as chemotherapy, targeted drug therapy, or immunotherapy within 7 days prior to the ablation procedure under study, and patients who had a systemic treatment plan such as chemotherapy, targeted drug therapy, immunotherapy, etc. before completing the primary efficacy endpoint assessment approximately 30 days after the ablation procedure.
15. Patients with uncorrectable coagulopathy based on investigator judgment.
16. Patients with a platelet count $\leq 50 \times 10^9/\text{L}$.
17. Patients who cannot discontinue antiplatelet medication (e.g., aspirin, clopidogrel, prasugrel, ticagrelor) at least **5 days** before the ablation procedure through **24 hours** post-procedure.
18. Patients who cannot discontinue anticoagulant medication (e.g., rivaroxaban, apixaban, dabigatran, edoxaban) at least **3 days** before the ablation procedure through **24 hours** post-procedure.
19. Patients who cannot discontinue warfarin before at least **5 days** before the ablation procedure of the study or have an INR > 1.5 .
20. As judged by the investigator, the patient has hypertension that cannot be effectively controlled by pharmacological treatments.
21. Severe hepatic, renal, cardiac, pulmonary or cerebral insufficiency, severe anemia, dehydration, and severe nutrition and metabolism disorders, which cannot be corrected or improved within a short term; or serious systemic infection; or severe neuromuscular diseases.
22. Expected survival less than 6 months.
23. Participation in any other interventional clinical study within 30 days before screening.
24. Physical or psychological condition which would impair study participation.
25. Patient is judged unsuitable for study participation by the investigator for any other reason.

Intra-Ablation Exclusion Criteria:

26. Before ablation probe puncture on the skin, patient is judged unsuitable for study participation due to intolerance to anesthesia.
27. Before ablation probe puncture on the skin, patient is judged unsuitable for study participation due to presenting any other condition.

3) Criteria of and procedure of Study Discontinuation

The criteria for Subject's Discontinuation from Study include, but are not limited to:

1. Subject withdraws the informed consent: Subject decides to withdraw from the study. This decision must be an "independent decision" and should be recorded in the subject's study files;
2. Investigator's decision: According to reasonable medical determination, the investigator can decide that allowing the subject to withdraw from this study serves the subject's best interests (including subject's discontinuation from the study due to the procedure being stopped before the ablation began);
3. Adverse events (AE)/serious adverse events (SAE): AE/SAE may not cause the subject to terminate this study. If the investigator decides to terminate a subject from the study, this subject must be followed up, until the AE/SAE is resolved or until the stable clinical endpoint is reached or until the event is adequately explained.;
4. Subject died;
5. Lost to follow-up: all subjects should provide corresponding contact information and agree to participate in all planned clinical follow-ups. If the subject cannot return to complete the required clinical visit, then 3 telephone contacts should be attempted and ask the subject to return for the scheduled clinical visit. Each contact attempt should be recorded in the original medical record. If the subject does not respond to any of the 3 phone calls, the investigator must send the subject a registered letter or an express mail (EMS) that can record the sending and receiving information. If the subject does not respond to the registered letter or EMS, and no further contact is made, this subject should be regarded as having missed the scheduled visit. If the above contact attempts still fail in 1 month after the ending of last scheduled visit, then this subject will be regarded as lost to follow-up; at this time, the electronic case report form (e-CRF) at the end of study must be filled in;
6. The sponsor discontinues the study;
7. The health authorities request study termination.

Procedure for subject's discontinuation from the trial:

If the subject discontinues the study, the reasons for termination will be documented in the source document and site files and submitted via the eCRF.

For a subject that discontinues the study due to procedure stop before ablation power emitting and

after probe puncture on the skin, there will be a new subject enrolled as a replacement. No replacement plan for other discontinued subjects.

Criteria of Sponsor's Discontinuation of the Trial:

Sponsor has the rights to temporarily suspend/discontinue or prematurely terminate studies of a single site, multiple sites or all sites for reasons including but not limited to: safety issues, ethical issues, administrative issues, inaccurate or incomplete data records, non-compliance, the quality or quantity of recruited subjects is not satisfactory.

Flow of Sponsor's Discontinuation of the Trial:

If the sponsor decides to suspend or terminate the clinical trial, it shall notify the medical device clinical trial management departments of all the clinical trial institutions according to regulatory requirements and provide reasons in writing. The departments shall promptly notify corresponding investigators and ethics committees. Suspended clinical trials shall not be resumed without the approval of the ethics committees.

4) Time of enrollment

Subjects are considered as being enrolled when they have completed the followings:

- Completion of the informed consent process;
- The investigator determines that the subject has met all the inclusion criteria without meeting any exclusion criteria.

Before the informed consent is signed, no study-related operating procedures can be implemented.

5) Expected overall duration of clinical trial and reasons for determination

The expected overall duration is approximately 40 months, including ethics committee meeting, agreement signing, subject enrollment and follow-up, data management, statistical analysis, writing final clinical report, etc.

6) Expected duration of participation of each subject

According to the Schedule of Activities specified in the protocol, the duration of each subject's participation in the study will be 13 months (about 1 month for Screening and 12 months for follow-up). The follow-up schedule will be based on the original ablation procedure date. A re-ablation for any reason will not change or extend the follow-up visit schedule.

7) Number of subjects required for clinical trial

This study plans to enroll 120 subjects plus run-in subjects (each site will enroll 2 run-in subjects). Because this is a single-arm study, there will be no randomization of subjects. See Section 8 "Sample size calculation" for this sample size selection basis

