7.1.8. Safety Evaluation Method

1) Description of safety parameters

Safety parameters include:

- All AEs from the start of any ablation procedure (from the probe puncture on skin) to 30 days post-ablation or early discontinuation.
- All SAEs from the start of ablation procedure through the end of the study or early discontinuation.
- All device-related AEs, procedure-related AEs, device-related SAEs and procedure-related SAEs from the start of ablation procedure through the end of the study or early discontinuation.

The incidence of the prespecified AEs below will also be summarized and reported:

1. Pneumothorax (all and those requiring chest tube drainage)
2. Hemorrhage (all and those requiring treatment)
3. Post-ablation syndrome
4. Chest wall pain
5. Pleural effusion (all and those requiring chest tube drainage)
6. Pneumonia
7. Lung or chest abscess
8. Other infections
9. Bronchopleural fistula

2) Selection of method and time to evaluate, record, and analyze the safety parameters

From the time of signing the informed consent form until approximately 30 days (Visit 3) after ablation (including primary and repeat ablation) or early discontinuation, all adverse events will be recorded. During this period, all adverse events from the start of ablation (i.e., probe puncture on the skin) will be reported.

After approximately 30 days (Visit 3) post ablation, adverse events considered by the investigator as related to the study device or/and study procedures and all serious adverse events will be recorded and reported till the end of the study or early discontinuation.

For subjects who stop ablation and withdraw from the study without ablation power emission while the needle has punctured the skin during the ablation procedure, the subject will be followed up for safety events up to 30 days after the procedure. If the discontinued subject reports a serious adverse event, the subject will be followed until event resolution, stabilization, or until the event is adequately explained.

The safety parameters will be recorded on the e-CRF according to the investigator's record, medical record, and all other related source documents collected at each follow-up visit.

See Section 8 for safety endpoint analysis methods.

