- Progression at other site to be evaluated by a study physician or may be reported by a patient's primary treating oncologist. If there is a progression, the study physician should specify if the progression is a new lung malignant tumor, or a distant metastasis.
- Any unplanned hospitalization in any hospital for any reason within 30 days post-ablation will be recorded, and the investigator will assess the reason for re-admission and record it in the study database.
- Relevant concomitant medication: including blood thinning/anticoagulants, antineoplastic agents such as chemotherapy/ targeted therapy/ immunotherapy, steroids, anti-inflammatories, NSAIDs, antibiotics and medications used to treat relevant medical history and adverse events.
- Concomitant procedure: the name, time, site and purpose of the concomitant procedure (including but not limited to puncture, radiotherapy, ablation therapy and surgical resection).
- All AEs and SAEs.

Note: Within the study, re-ablations on the initially ablated target tumor(s) should not be performed before the Visit 3 assessment for Technical Efficacy has been completed. If investigators assess it is medically indicated/necessary to re-ablate before the Visit 3 Technical Efficacy assessment, the re-ablated tumor's Technical Efficacy assessment will be counted as failure. The re-ablation will not change or extend the subject's follow-up schedule.

4) Visit 4 to visit 6 (end of study)

Visit 4 will occur at 3 months (\pm 14 days), Visit 5 will occur at 6 months (\pm 1 month), and Visit 6 will occur at 12 months (\pm 1 month) after surgery during which subjects will return to the study site for the following assessments:

- ECOG performance status score.
- Quality of Life questionnaire: the QOL questionnaires include the EORTC QLQ-C30 and the lung-specific QLQ-LC13 (Visits 5 and 6 only).
- Enhanced CT scan of the lung.
- Document the investigator's determination of Local Tumor Progression.

- Submit the CT images to the IRC for determination of whether Local Tumor Progression has occurred or not.
- Progression at other site to be evaluated by a study physician or may be reported by a patient's primary treating oncologist. If there is a progression, the study physician should specify if the progression is a new lung malignant tumor, or a distant metastasis.

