- Relevant concomitant medication: including antineoplastic agents such as chemotherapy/targeted therapy/immunotherapy and drugs related to the recorded adverse events.
- Concomitant procedure: the name, time, site and purpose of the concomitant operation (including but not limited to puncture, radiotherapy, ablation therapy and surgical resection).
- All AEs considered by the investigator as related to the study device or/and study procedures and all SAEs.

5) Unscheduled Visits

The following data will be collected at all unscheduled visits:

- Reason for the unscheduled visit.
- Relevant concomitant medication: Including antineoplastic agents such as chemotherapy/targeted therapy/immunotherapy and drugs related to the recorded adverse events.
- Concomitant procedure: the name, time, site and purpose of the concomitant operation (including but not limited to puncture, radiotherapy, ablation therapy and surgical resection).
- All AEs and SAEs.
- Any other study assessments, per SOC.

Notes: Re-ablations on the target tumor(s) in the study should only be conducted after finishing Visit 3 evaluation.

Re-ablations using the microwave ablation system and ablation probe provided in this study can only be performed when there is local progression of lung tumor after initial ablation, or residual tumor or insufficient margin during initial ablation of tumor (if considered medically indicated/necessary by the investigator so as to obtain sufficient ablation margin of tumor). The study device provided by this study cannot be used for the ablation of other lesion foci.

For each re-ablation using the study device within this study, the following information will be captured:

- Reason for the re-ablation.

- Record ablation procedure details, including but not limited to the following:
 - Procedure date and time
 - Mode of anesthesia
 - Guidance method used
 - Anatomic location of ablated tumor
 - Number of ablation cycles
 - Ablation power and time
- Device count: all probe types and amounts.
- Document the investigator's re-ablation result evaluation.
- Submit the CT to IRC for re-ablation result evaluation.
- All AEs and SAEs.

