### **8.11.6 Re-admission rate**

The Re-admission Rate is defined as the percentage of subjects with any re-admission to the hospital within 30 days post-ablation (including the original ablation or a repeat ablation). The number and percentage of subjects with re-admissions will be summarized, along with the reasons for re-admission.

Listings will be provided for those with any re-admission.

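### The 30-day all-AE rule and the re-admission endpoint both cover repeat ablations, but the Visit 4–6 checklist, Section 14.5 and the Visit 3-only re-admission item do not, so collection in re-ablated subjects may be incomplete

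*Protocol*

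**What the plan says.** **What is to be measured.** Protocol Section 7.1.8 defines the first safety endpoint as "All AEs from the start of any ablation procedure (from the probe puncture on skin) to 30 days post-ablation or early discontinuation". Its recording rule runs "until approximately 30 days (Visit 3) after ablation (including primary and repeat ablation) or early discontinuation, all adverse events will be recorded". The same rule stands in the synopsis (Safety Assessments), in Table 1 note 22 and in Section 14.1. The re-admission endpoint (synopsis, Section 7.1.7) counts AE-caused unplanned admissions after the original or a repeat ablation. SAP 8.11.6 counts any re-admission "within 30 days post-ablation (including the original ablation or a repeat ablation").

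**When contacts occur.** Section 7.1.5, item 6, ties follow-up to the original ablation date: "A re-ablation for any reason will not change or extend the follow-up visit schedule". The Visit 3 note in Section 7.2.3 repeats this. The notes under Unscheduled Visits add: "Re-ablations on the target tumor(s) in the study should only be conducted after finishing Visit 3 evaluation".

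**What is asked at those contacts.** The Visit 4–6 checklist in Section 7.2.3 takes "All AEs considered by the investigator as related to the study device or/and study procedures and all SAEs". Section 14.5 sets the same limit on reporting from Visit 3 to the end of the study and makes no exception for a repeat ablation. The hospitalization item, "Any unplanned hospitalization in any hospital for any reason within 30 days post-ablation will be recorded", appears in the Visit 3 procedures. It is not in the lists for Visits 4–6, unscheduled visits or re-ablation. Table 1 likewise marks re-admission at one visit only.

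**The concern.** The recording rule labels its 30-day limit as Visit 3, but Visit 3 exists only for the initial ablation and is meant to precede any re-ablation. A site working from the Visit 4–6 checklist and Section 14.5 would leave out some events that the safety endpoint counts. A site working from Section 7.1.8 would record them. Both would be following the protocol.

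The re-admission question is normally asked before a re-ablation can have happened, although the endpoint includes re-ablations. What is at stake is how complete the safety and re-admission data are after repeat treatment of the same tumor. A low count there could partly reflect what sites were asked. An analysis rule in the SAP cannot recover events that were never recorded.

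**Working it through.** No stated figure is in dispute. The check sets the collection instructions side by side and then does the visit arithmetic.

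**1. Instructions that apply after a re-ablation**

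| Place | AE scope | Names repeat ablation? | Asks about re-admission? |
|---|---|---|---|
| Synopsis, Table 1 note 22, Sections 7.1.8 and 14.1 | All AEs to about 30 days | Yes | No |
| Visit 4–6 checklist, Section 7.2.3 | Related AEs, all SAEs | No | No |
| Section 14.5, after Visit 3 | Related AEs, all SAEs | No | No |
| Unscheduled-visit list | All AEs and SAEs | Not in the AE item | No |
| Re-ablation capture list | All AEs and SAEs, no time window | Yes | No |
| Visit 3 procedures | All AEs and SAEs | No | Yes |

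**2. Which data are exposed**

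- *Non-serious AEs judged unrelated.* They fall under the first row but not the second or third. The unscheduled-visit list helps only if such a visit takes place. Medication records would not reveal them either: Visits 4–6 record antineoplastic agents and drugs for AEs already recorded, whereas Visit 3 also takes antibiotics, steroids and NSAIDs.
- *Re-admissions not caused by an AE.* An AE that requires in-patient care is an SAE (Section 14.2), so AE-caused admissions should reach the database. Section 14.2 keeps disease progression and planned hospitalization for a pre-existing condition out of the SAE count. SAP 8.11.6 counts any re-admission, so an admission for progression would count there with no item to collect it.
- *The end of the window, when Visit 6 comes first.* See step 3.

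**3. Visit calendar**

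Assumed days for Visits 3, 4, 5 and 6: nominal 30, 90, 180, 365; all early 23, 76, 150, 335; all late 37, 104, 210, 395. Possible re-ablation days run from Visit 3 to Visit 6 inclusive.

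- Possible days = V6 − V3 + 1.
- Days with a scheduled visit 23–37 days later (30 ± 7) = 15 per visit × 3 visits = 45.
- Days whose 30-day window runs past Visit 6 = 30.

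| Calendar | Possible days | Visit at 30 ± 7 days | Window cut off by Visit 6 |
|---|---|---|---|
| Nominal | 365 − 30 + 1 = 336 | 45/336 = 13.4% | 30/336 = 8.9% |
| All early | 335 − 23 + 1 = 313 | 45/313 = 14.4% | 30/313 = 9.6% |
| All late | 395 − 37 + 1 = 359 | 45/359 = 12.5% | 30/359 = 8.4% |

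On the nominal calendar, a re-ablation on the day after Visit 5 (day 181) has its window end on day 211. The next scheduled visit is 365 − 211 = 154 days later. The longest wait from the end of a window to the next scheduled visit is 184 days (re-ablation on day 151, window end on day 181, 365 − 181 = 184), but there Visit 5 falls one day before the window closes. Both figures are the same on all three calendars. These are shares of calendar days, not of patients.

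**4. How many subjects**

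The documents give no re-ablation rate. As an illustration only: at the planned 90% Technical Efficacy, with one tumor per subject, 0.10 × 120 = 12 subjects would have residual tumor at Visit 3. If half to all of them were re-ablated, that is 6–12. Re-ablation for later progression would add to this. The 10% local progression in the colorectal-metastasis series cited in Section 4.2 does not transfer well: its median follow-up was 25.6 months and its tumors measured up to 3.2 cm, against 12 months and 2 cm here.

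**The case against.** The strongest reply is that collection is already required. Four places order all AEs to be recorded for about 30 days after primary and repeat ablation. Table 1 marks AEs at every visit and ties that row to note 22, so the Visit 4–6 checklist is not the only instruction at those visits. The re-ablation and unscheduled-visit lists take all AEs and SAEs. A fixed visit schedule does not forbid recording or extra visits. Every re-ablation at least 30 days before Visit 6 has a scheduled visit at or after the end of its window.

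Complications of the procedure should also count as related AEs or SAEs, which are collected throughout. Section 14.1 classes events whose relatedness cannot be assessed as possible. Section 7.1.7 bases the re-admission rate on investigator records without naming a visit.

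Most of this stands. A reader might infer that no contact collects the period, that the data are missing by design, that complications of repeat treatment go unrecorded, or that the re-admission rate is really a rate for the initial ablation. The documents support none of these.

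The conflict itself remains. The re-ablation list gives no time window, the checklist and Section 14.5 omit the exception, and re-admission is asked once. By contrast, a subject stopped after puncture and before power emission has an explicit 30-day safety follow-up (Section 7.1.8). The eCRF is not among the documents, so it cannot be judged whether it already collects hospitalization.

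**Conclusion.** The point holds as an inconsistency that may leave collection incomplete in re-ablated subjects. It affects non-serious AEs judged unrelated, re-admissions not caused by an AE (which matter only under the SAP definition), and windows cut off by Visit 6.

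Only about 13–14% of possible re-ablation days have a scheduled visit near day 30, and about 8–10% have a truncated window. These shares rest on the assumed visit days and say nothing about when re-ablations would actually occur. The number of subjects is unknown, and 6–12 is an illustration.

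The effect is confined to secondary safety endpoints and the exploratory re-admission rate. The primary endpoint is read at Visit 3, and the 108 evaluable and 120 enrolled subjects do not depend on re-ablation data. The SAP's 30-day AE summary (8.10.7) is anchored to the initial ablation only. The exposed AEs would therefore be missing from the overall AE summaries and listings, not from a dedicated re-ablation table.

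**What to change.** 1. Reconcile the Visit 4–6 checklist (Section 7.2.3) and Section 14.5 with Sections 7.1.8 and 14.1 by adding to both: *and all AEs within 30 days after any study-device re-ablation*.
2. Add the unplanned-hospitalization item to the re-ablation capture list and to Visits 4–6, mark it in Table 1, and align the re-admission definitions in protocol Section 7.1.7 and SAP 8.11.6.
3. Preferably collect both by one data-collection phone contact about 30 days after each study-device re-ablation. The protocol already accepts the phone for pain scores. Efficacy visits stay tied to the initial ablation.
4. For re-ablations within 30 days of Visit 6, either report the window as truncated or extend safety collection by amendment. The second option exceeds the 13 months of participation in Section 7.1.5 and would probably need revised consent. It is not essential to the fix.

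The cost is protocol and eCRF wording, a small number of phone contacts, and an amendment with ethics review.
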